8.3.2.3 Assessment of Severity (Intensity)

The severity of an adverse event is defined as a qualitative assessment of the level of discomfort of an adverse event as is determined by the Investigator or reported to him/her by the subject. The assessment of intensity is made irrespective of study medication relationship or seriousness of the event. The investigator will make an assessment of intensity for each AE and SAE reported during the study and assign it to 1 of the following categories: and should be evaluated according to the scale in Table 3.

Table 3: Assessment of Severity (Intensity)

Mild	An event that is easily tolerated by the participant, causing minimal discomfort and not interfering with everyday activities.
Moderate	An event that causes sufficiently discomfort and interferes with normal everyday activities.
Severe	An event that prevents normal everyday activities. An AE that is assessed as severe should not be confused with a SAE. Severe is a category utilized for rating the intensity of an event; and both AEs and SAEs can be assessed as severe.

Please note: the term “severe” is used to describe the intensity (severity, see above) of an event/reaction; the event/reaction itself may be of relatively minor medical significance (such as severe headache). This is not the same as a “Serious” Adverse Event, which is based on subject/event outcome or action criteria usually associated with events that pose a threat to the subject’s life or vital functions. “Serious” (NOT severity) serves as a guide for defining regulatory reporting obligations. An event is defined as ‘serious’ when it meets at least 1 of the predefined outcomes as described in the definition of an SAE, NOT when it is rated as severe.

8.3.4 Follow-up of subjects after adverse events

If an adverse event/adverse reaction occurs, the Investigator will institute support and/or treatment as deemed appropriate. If a non-serious adverse event/adverse reaction is unresolved at the time of the last visit, efforts will be made to follow up until the adverse event/adverse reaction is resolved or stabilized, the subject is lost to follow-up, or there is other resolution to the event.

9 Statistics

9.1 Primary Hypotheses

H₀₁: The percentage of subjects with no pain within 5 minutes is NOT different between subjects treated with AG-920 and Placebo.

H₁₁: The percentage of subjects with no pain within 5 minutes is different between subjects treated with AG-920 and Placebo.

9.2 Sample Size Considerations

Efficacy:

With 60 subjects per treatment group and assuming 15% response in the placebo group, this study will have 88% power to detect a treatment effect of at least 25% between AG-920 and placebo ($\alpha=0.05$, two-sided).

9.3 Analysis populations

Randomized Population: The randomized population will include all subjects who were randomized to treatment. Baseline (screening) variables and demographic characteristics will be summarized for this population.

Intent-to-Treat Population (ITT): The ITT population will include all randomized subjects who have received at least one dose (2 drops) of study medication. This population will be the primary population for the efficacy analyses and all efficacy variables will be summarized using this set of subjects. The ITT population will include subjects as randomized.

Per-protocol population (PP): The PP population is a subset of the ITT population, which will include those subjects (and their visits) who do not have major protocol violations likely to seriously affect the primary outcome of the study as judged by a masked evaluation prior to the unmasking of the study treatment. This population will be the secondary population for efficacy

analyses and all efficacy variables will be summarized using this set of subjects. If the PP and ITT populations are exactly the same and there are no missing data, then additional efficacy analyses on the PP population will not be performed. The PP population will include subjects as treated.

Safety Population: The safety population will include all randomized subjects who have received at least one dose (2 drops) of study medication. This population will be used to summarize the safety variables and will summarize subjects as treated.

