2 OBJECTIVES AND ENDPOINTS

Primary Objective

To evaluate anesthetic efficacy of AG-920

Secondary Objectives

To evaluate how long it takes one dose of AG-920 to anesthetize the eye

To evaluate how long one dose of AG-920 anesthetizes the eye

To evaluate the safety and tolerability of AG-920

Primary Endpoints

The proportion of subjects with no pain at 5 minutes.

Secondary Endpoints

Mean time to no pain score (onset)

Mean duration of anesthetic effect

Visual acuity, biomicroscopy, AEs, TEAEs, SAEs, withdrawals due to TEAEs

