### **2.9.3 Safety analysis**

#### Treatment Exposure

Frequencies of exposure to the study medication will be calculated based on the number of drops the subject has received over the course of the study. Frequencies of exposure will be categorized as the following: 1 drop and 2 drops. Frequencies of exposure will be summarized by treatment for the safety population defined in Section 3.1, as well as for each gender group.

Compliance rates will be calculated by dividing the number of drops received by the number of drops that should have been given during the application of dose. Compliance rates will be summarized.

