### Safety Population

The safety population is defined as all subjects who are randomized and who have received at least one drop of the dose (2 drops) of the study medication. The safety population will be utilized for comparative safety analyses among treatment groups.

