### Intention-to-treat (ITT) Population

This population is defined as all subjects who are randomized to treatment and have received at least one dose (two drops) of the study medication. The ITT population is the primary population for efficacy evaluation in this study. Treatment identification is defined in the ITT population by treatment assignment. The ITT population will be identified and finalized before the database is locked and the study is unmasked.

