### Per-Protocol (PP) Population

This population is defined as sub-population of the ITT population. The PP population is the secondary population for efficacy evaluation in this study and will be defined as all randomized subjects who completed the study treatment with no major protocol violations likely to seriously affect the primary outcome of the study as judged by a masked evaluation prior to the unmasking of the study treatment. In case there is a difference between treatment assigned and received, treatment actually received will be utilized to define the treatment identification in the PP population. In case there are missing data in efficacy measures, the analysis of the PP population will be based on observed or actual data only (without imputation). The PP population will be identified and finalized before the database is locked and the study is unmasked.

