## **3.2 Screening and Enrollment**

A screening summary including the number of subjects screened for study participation will be presented by site (Table 1.1.1).

An enrollment summary including the number of subjects enrolled, randomized, and completed the study will be presented for all enrolled subjects and by site (Table 1.1.2). Enrolled subjects include those individuals who are screened and returned to the clinic on Day 1 and randomized into the study. The number of subjects treated with at least one drop of the dose (2 drops) of the study medication (i.e., the safety population) will be summarized for each treatment group and overall (Table 1.1.3). The number of subjects treated with at least one dose (2 drops) of the study medication (i.e., the ITT population) will be summarized for each treatment group and overall (Table 1.1.4). The number of subjects in the PP population will be summarized for each treatment group and overall (Table 1.1.5).

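### The protocol's Safety population requires two drops and the SAP's requires one, so a subject who stops after the first drop is in one Safety set and not in the other

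*Protocol*

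**What the plan says.** **Safety population.** Protocol 9.3: "The safety population will include all randomized subjects who have received at least one dose (2 drops) of study medication". The same paragraph says that subjects are summarized as treated. The SAP (3.1, Safety Population) instead takes "all subjects who are randomized and who have received at least one drop of the dose (2 drops) of the study medication", and SAP 3.2 repeats the one-drop threshold for Table 1.1.3. SAP 2.9.3 (Treatment Exposure) builds on it: "Frequencies of exposure will be categorized as the following: 1 drop and 2 drops". SAP 5.1 tabulates those categories for the Safety population. The SAP's Safety definition gives no as-treated rule. It writes such a rule for the per-protocol set only: "treatment actually received will be utilized to define the treatment identification in the PP population".

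**Safety endpoints.** Protocol 2 lists "Visual acuity, biomicroscopy, AEs, TEAEs, SAEs, withdrawals due to TEAEs".

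**ITT population.** Here the documents agree. Protocol 9.3: "The ITT population will include all randomized subjects who have received at least one dose (2 drops) of study medication". SAP 3.1: "all subjects who are randomized to treatment and have received at least one dose (two drops) of the study medication". SAP 2.9.1 says the same of the primary analysis. The protocol's separate Randomized Population is used only for baseline and demographic summaries.

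**Related SAP outputs.** SAP 3.7 plans Listing 4 for ITT members who lack two drops, a post-dose pinch assessment, or both. SAP 4.2 plans compliance tables for the Safety set (1.5.2) and the ITT set (1.5.3), with compliance defined in SAP 2.9.3 as drops received divided by drops due.

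**The concern.** A Safety set should hold everyone exposed to study drug. The subject at issue is one who receives the first drop and stops before the second, perhaps because of it: Protocol 1.2 names stinging or burning on instillation as an expected risk. That subject belongs to the SAP's Safety set and not to the protocol's. The count and the denominator of a stated safety endpoint therefore depend on which document is followed, and neither contains a precedence clause. Protocol 9.4.1 says only that the SAP will describe the methods more fully.

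There is a secondary efficacy point. Because both documents require two drops for ITT, no planned efficacy analysis covers all randomized subjects. LOCF (Protocol 9.5, SAP 2.8) cannot bring a one-drop subject in, because every pinch is timed from the second drop (SAP 2.2) and that subject has no pinch result to carry forward.

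**Working it through.** **1. Definitions side by side.**

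| Subject | Protocol Safety | SAP Safety | ITT (both documents) |
|---|---|---|---|
| Randomized, no drop | out | out | out |
| Randomized, one drop | **out** | **in** | out |
| Randomized, two drops | in | in | in |

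Only the middle row differs. Under the protocol rule the SAP's one-drop exposure row must be zero.

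**2. Size of the Safety difference.** The documents give no one-drop rate, so the count k is an assumption. Suppose 60 AG-920 subjects receive at least one drop, k of them stop after one drop and withdraw for an adverse event, and nobody else withdraws. The SAP rate is k/60 and the protocol rate is 0/(60 − k).

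| k | SAP | Protocol |
|---|---|---|
| 0 | 0/60 | 0/60 |
| 1 | 1/60 = 1.7% | 0/59 |
| 2 | 2/60 = 3.3% | 0/58 |
| 3 | 3/60 = 5.0% | 0/57 |

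Events in two-drop subjects hardly move. Three such events with k = 3 are 3/60 = 5.00% against 3/57 = 5.26%.

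**3. Where the one-drop subject still appears.** In the protocol: disposition (9.4.4) and data listings (9.7). In the SAP: Table 4.1.1, an overall adverse-event summary for study participants (5.3), who are defined in 3.1 as all subjects with randomization completed; Listing 3, for all randomized subjects (3.6); and the listings and narratives for withdrawals due to adverse events (2.9.3, 5.3).

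**4. The two SAP outputs.** Every ITT member has two drops by definition, so the missing-drops condition of Listing 4 has no members. Its missing-pinch condition still works. Compliance is 2/2 = 100% for every ITT member, so Table 1.5.3 can show nothing else. A one-drop subject has 1/2 = 50% and can appear only in Table 1.5.2.

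**5. The plan's power figure.** Inputs (Protocol 9.2, SAP 2.5): 60 per arm, 15% against 40%, two-sided 0.05, chi-square without continuity correction.

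- Pooled rate = (0.15 + 0.40)/2 = 0.275.
- Null SE = √(2 × 0.275 × 0.725/60) = 0.0815.
- Alternative SE = √((0.15 × 0.85 + 0.40 × 0.60)/60) = 0.0783.
- Power = Φ((0.25 − 1.96 × 0.0815)/0.0783) = Φ(1.153) = 87.6%. Exact enumeration gives 88.6%.

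The stated 88% reproduces.

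**6. Size of the ITT point.** Assume 40% and 15% among two-drop subjects, and two one-drop subjects in an arm counted as not anesthetized. The arm's rate becomes rate × 58/60: 0.40 × 58/60 = 38.67% for AG-920 and 0.15 × 58/60 = 14.50% for placebo. The two-drop set gives 25.0 points in every case. Exact power is shown as two-drop set, then all randomized, with the one-drop subjects as fixed non-responders. CMH assumes 30 subjects per arm per eye and one one-drop subject per eye in each affected arm.

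| One-drop subjects | Difference, all randomized | Pearson (Protocol 9.4.6) | CMH by eye (SAP 2.9.1) |
|---|---|---|---|
| 2 AG-920 | 38.67 − 15.00 = 23.7 points | 88.1% → 85.5% | 87.6% → 84.9% |
| 2 placebo | 40.00 − 14.50 = 25.5 points | 87.3% → 90.0% | 87.4% → 89.6% |
| 2 in each arm | 38.67 − 14.50 = 24.2 points | 87.3% → 87.2% | 87.3% → 86.7% |

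The estimate moves by −1.3 to +0.5 points.

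**The case against.** The best defense is that the practical exposure is slight. Staff give both drops 30 seconds apart, subjects are screened for tolerating an artificial tear, and Protocol 9.5 expects little missing data. The SAP holds the table plan and already has the more inclusive Safety rule, and Protocol 9.6 requires departures from the statistical plan to be explained. The zero counts in the protocol column arise only if the protocol's definition is used in place of the SAP's. Most of this stands. It limits the size of the problem but does not remove the contradiction, and the tear screen tests neither the study drug nor its vehicle.

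Four stronger readings are tempting, and the documents do not support them:

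- *A one-drop subject disappears from safety reporting.* The outputs in step 3 show otherwise. The loss is confined to summaries built on the protocol's Safety set.
- *The SAP contradicts the protocol on as-treated analysis.* The SAP is silent, and silence does not override the protocol.
- *The ITT definition is an error or biases the primary result.* Both documents state the two-drop rule openly and agree on it. Whether to call the set modified ITT is mainly a matter of naming, and the direction of any effect is unknown.
- *Listing 4 and Table 1.5.3 are unusable.* One condition of the listing still works. The table is redundant, and its informative Safety counterpart exists.

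**Conclusion.** The Safety definitions conflict and need to be reconciled before unmasking. This is a modest point, limited to the Safety definition and two SAP table-plan corrections. It has an effect only if at least one subject stops between drops. Under the assumed range of one to three AG-920 withdrawals, the reported rate is 1.7% to 5.0% under the SAP and zero under the protocol. The sample size is not in question. The lack of an efficacy analysis in all randomized subjects is secondary: with two one-drop subjects in either or both arms, the estimate stays within about 1.3 points of the design difference. Those figures depend on the assumed counts, the design response rates and, for CMH, an even split by eye. They leave out any undosed randomized subjects, whose number the documents do not give.

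**What to change.** 1. **Main change.** Amend the Safety definition in Protocol 9.3 to at least one drop, matching the SAP, and keep its as-treated rule. Repeat as treated in the SAP 3.1 Safety definition. Cost: one sentence in each document, but the protocol sentence needs an approved amendment under Protocol 12.4.

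2. **Optional.** Keep the two-drop set as primary and add one sensitivity analysis of the primary endpoint in all randomized subjects, as randomized. Use the same test as the primary analysis in whichever document governs, so that only the population changes. The protocol's Pearson test and the SAP's CMH test must be reconciled separately. Count subjects whose dosing was not completed, including undosed subjects, as not anesthetized. Apply the existing LOCF rule to two-drop subjects who lack the 5-minute pinch. Cost: one table and short text in Protocol 9.4.6 and SAP 2.9.1. The primary analysis and its power do not change. Relabeling the set as modified ITT is also optional. If done, it must be carried through every section of both documents that uses the term, which is the larger editing job.

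3. **Tidy up the SAP.** Define Listing 4 (SAP 3.7) as randomized subjects without two drops, plus ITT subjects without a pinch result. Drop Table 1.5.3 (SAP 4.2) or run it on all randomized subjects. Cost: wording only.

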9.4 Statistical methods to be employed

9.4.1 General Considerations

All continuous study assessments will be summarized by treatment and time point (as applicable) using descriptive statistics (n, mean, median, standard deviation, minimum, and maximum). All categorical study assessments will be summarized by treatment and time point (as applicable) using frequency counts and percentages.

Hypothesis testing, unless otherwise indicated, will be performed at a two-sided 0.05 significance level. Where applicable, two-sided 95% confidence intervals will be reported. All p-values will be displayed to four decimal places, with p-values less than 0.0001 presented as '<0.0001' and p-values greater than 0.9999 presented as '>0.9999'. Difference between Articaine Sterile Topical Ophthalmic Solution (AG-920) and Placebo will be calculated as Articaine Sterile Topical Ophthalmic Solution –Placebo.

All study data will be listed by treatment, subject, time point, and eye (as applicable).

Statistical methods will be more fully described in a separate document (Statistical Analysis Plan).

9.4.2 Interim analyses

There is no planned interim analysis.

9.4.3 Analysis of Baseline Data

Demographic and baseline characteristics such as age, sex, ethnicity, race, and iris color will be summarized and listed. Depending upon the extent of medical and ocular history and concomitant medications in these healthy subjects, coding systems such as MedDRA and WHODrug will be used, and these data will be summarized and listed.

9.4.4 Subject Disposition

Subject enrollment and exit status (completed or discontinued) will be summarized and listed.

9.4.5 Protocol Deviations

Important protocol deviations are deviations from the protocol that potentially could have a meaningful impact on study conduct, or on the primary efficacy or key safety outcomes for an individual subject. The criteria for identifying important protocol deviations will be defined within the appropriate protocol-specific document. Important protocol deviations will be reviewed as part of the ongoing data cleaning process and all important deviations will be identified and documented prior to unmasking to confirm exclusion from analysis sets. Further details will be provided in the SAP.

9.4.6 Analysis of Efficacy

Analyses will be performed primarily on the ITT population and will be repeated on the PP population to determine robustness of results. For the primary efficacy endpoint of the proportion of subjects with no pain at 5 minutes, a Pearson chi-square test will be used for the comparison of the two proportions from the two treatment groups. In addition, a two-sided 95% confidence interval for the difference in response rates between the two treatment groups will be calculated. If the lower limit of the 95% confidence interval is greater than 0 and the P value is statistically significant ($P < 0.05$), then superiority of AG-920 over the placebo will be claimed.

Sub-group analyses based upon pre-study characteristics such as sex, iris color, age, and race may be completed to further investigate the efficacy and safety measures.

9.4.7 Analysis of Safety

Slit lamp biomicroscopy and external eye exam measures will be summarized at each measured time point using discrete summary statistics.

Visual Acuity data will be summarized at each time point using both continuous summaries (Logarithmic Minimum Angle of Resolution, logMAR), including change from baseline, and discrete summaries, including change from baseline in the number of lines and the proportion of subjects with a worsening of ≥ 3 lines from baseline.

9.4.8 Adverse Events

Verbatim descriptions of AEs will be mapped to MedDRA thesaurus terms and be presented in a data listing. Treatment emergent AEs, those that occur after the first dose of study medication, will be summarized by treatment group using frequency counts and percentages for each system organ class (SOC) and preferred term (PT) within each SOC. Summaries will be presented separately for ocular and non-ocular AEs. These summaries will also be presented by the relationship to the Investigational Medical Product (related, unrelated) and by severity of the AE (mild, moderate, severe). Fisher's exact test will be used to test the difference in proportions of subjects with each AE between treatment groups (SOC and PT).

9.5 Procedure for accounting for missing, unused, or spurious data

A minimal amount of missing data is expected in this study because of the short duration and the subjects being in the clinic on Day 1. For the ITT population, any missing data on Day 1 will be imputed using the method of last observation carried forward (LOCF), where the closest non-missing value prior to the missing value will be carried forward and imputed for the missing value. The PP and Safety populations will be based on observed data only (without imputation). Any missing, unused, or spurious data will be noted and explained in the final statistical report.

9.6 Procedure for reporting deviations from the statistical plan

Any deviations from the statistical plan will be described and a justification given in the final statistical report.

9.7 Data listings

Data listings will be prepared for all data on the database.

10 QUALITY CONTROL AND QUALITY ASSURANCE

10.1 Audit and Inspection

Study centers and study documentation may be subject to Quality Assurance audits during the study by the Sponsor or its designee. In addition, inspections may be conducted by regulatory authorities at their discretion.

10.2 Direct Access to Source Data Documents

Authorized representatives of the Sponsor, a regulatory authority, an IEC or IRB may visit the site to perform audits or inspections, including source data verification. The purpose of a Sponsor audit or inspection is to systematically and independently examine all study-related activities and documents to determine whether these activities were conducted, and data were recorded, analyzed, and accurately reported according to the protocol, GCP guidelines, and any applicable regulatory requirements. The Investigator should contact the Sponsor immediately if contacted by a regulatory agency about an inspection.

10.3 Clinical Monitoring

Data for each subject will be recorded in a source document and in EDC for each subject who signs an informed consent form (ICF) and is administered IMP.

In accordance with current GCP and International Conference of Harmonisation (ICH) guidelines, the study monitor will carry out source document verification at regular intervals to ensure that the data collected in EDC are accurate and reliable.

The Investigator must permit the monitor, the IEC/IRB, the Sponsor's internal auditors, and representatives from regulatory authorities' direct access to all study-related documents and pertinent hospital or medical records for confirmation of data contained within EDC.

Due to the COVID-19 Pandemic, remote monitoring visits may replace some of the onsite monitoring visits. It will still be the responsibility of the monitor to discuss the study and any issues with the Principal Investigator via telephone or videoconference.

